6.2.2 Serious adverse events (SAEs)

A serious adverse event is any untoward medical occurrence or effect that

- results in death;
- is life threatening (at the time of the event);
- requires hospitalization or prolongation of existing inpatients' hospitalization;
- results in persistent or significant disability or incapacity;
- any other important medical event that did not result in any of the outcomes listed above due to medical or surgical intervention but could have been based upon appropriate judgment by the investigator.

An elective hospital admission will not be considered as a serious adverse event.

The investigator will report all SAEs to the sponsor without undue delay after obtaining knowledge of the events. The sponsor will report the SAEs through the web portal *ToetsingOnline* to the accredited METC that approved the protocol, within 7 days of first knowledge for SAEs that result in death or are life threatening followed by a period of maximum of 8 days to complete the initial preliminary report. All other SAEs will be reported within a period of maximum 15 days after the sponsor has first knowledge of the serious adverse events.

6.2.3 Suspected unexpected serious adverse reactions (SUSARs)

Not applicable

6.3 Annual safety report

Not applicable

6.4 Follow-up of adverse events

All AEs will be followed until they have abated, or until a stable situation has been reached.

Depending on the event, follow up may require additional tests or medical procedures as indicated, and/or referral to the general physician or a medical specialist.

SAEs need to be reported till end of study within the Netherlands, as defined in the protocol.

7. STATISTICAL ANALYSIS

7.1 Data description

Baseline characteristics will be presented using percentages for categorical covariates, means with standard deviations and/or medians with interquartile ranges for continuous variables. Comparison between baseline characteristics will be done using the chi-square test for categorical variables and Student's t-test or Mann Whitney-U test for continuous variables as appropriate. Based on a pilot study conducted at UHNT, we assume a patient dropout of 20% at 6 months follow up (see Sample size calculation). Baseline characteristics of patients who did and did not respond at 6 months follow up will be compared to examine whether selective dropout occurred. Multiple imputation will be performed in case of any missing data. Throughout the analyses, a *p*-value of 0.05 is considered statistically significant.

7.2 Primary study parameter(s)

The primary outcome, postoperative WHODAS 2.0 after 6 months, will be compared among patients with and without PMI, using Student's t-test or a nonparametric Mann Whitney U test. In case of normality, the mean 6-months WHODAS 2.0 will be calculated together with the accompanying 95% confidence intervals. Otherwise, the median WHODAS 2.0 with interquartile range will be reported.

With respect to the association between the different phenotypes of PMI (i.e. myocardial infarction, NITE and MAPE) and disability, the preoperative, postoperative and the change (meaning difference between pre- and postoperative measurements) in biomarkers are of particular interest. The biomarkers will be analyzed both as continuous variables and using predefined clinical thresholds to define when the each of the biomarkers are elevated.

Combination(s) of different biomarkers and the biomarker by itself in association with postoperative WHODAS 2.0 will be performed. These combination(s) of biomarkers will be related to one of the different phenotypes of PMI. Multivariable linear regression analyses will be performed to adjust for potential confounders including age, gender, comorbidities (cardiovascular risk factors), preoperative WHODAS 2.0 score, RCRI and surgical specialty.

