function, in patients with PMI and thereby, patients will be treated more appropriately and major complications could (hopefully) be prevented.

Nowadays, the Revised Cardiac Risk index (RCRI) is commonly used as a predictive tool to estimate the probability of MACE or mortality¹³. The RCRI includes six predictors, which are high risk surgery, history of myocardial infarction (MI), history of cerebrovascular disease, chronic heart failure, elevated creatinine and insulin dependent diabetes. Ford et al. performed a review on the performance of the RCRI in several validation studies and found that this cardiac index only moderately predicts, does not predict events in vascular surgery, and has not been prospectively validated using troponin or other biomarkers to predict MI or other cardiac events¹⁴. Since this publication, several studies reported the added predictive value to the RCRI of one (or more) biomarker(s), including (high sensitive) troponin¹⁵⁻¹⁷, (NT-pro)BNP^{15,16,18-20}, eGFR^{21,22}, CRP^{18,20}, ECG^{23,24} and transthoracic echocardiography^{19,25}. Addition of (high sensitive) troponin, (NT-pro)BNP and/or CRP to the RCRI seems promising for the prediction of MACE as the predictive performance significantly improves compared to the RCRI by itself. To our knowledge, different combinations of several biomarkers together in addition to the RCRI have not been reported yet.

Our primary objective is to investigate and compare the independent prognostic effect of the different PMI phenotypes (myocardial infarction and NITE) and noncardiac MAPE on disability. We will be diagnosing the differing PMI phenotypes using clinical evaluation and biomarkers. The primary endpoint is disability. Disability is assessed using the World Health Organization Disability Assessment Score 2.0 (WHODAS 2.0)²⁶. Our primary hypothesis is that any postoperative troponin elevation regardless of its association with MACE or noncardiac MAPE is independently associated with an increased risk of death and disability.

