2. OBJECTIVES

2.1 Primary objective

To investigate and compare the independent prognostic effect of the different PMI phenotypes (myocardial infarction and NITE) and noncardiac MAPE on disability in patients undergoing elective noncardiac surgery.

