4.4 Sample size calculation

For this study, we aim to include 500 patients at the UMCU in this study. A similar study will be conducted at the University Health Network Toronto (UHNT), Toronto, Canada and they will include 500 patients with the same in- and exclusion criteria. After including all patients in both centers, we will combine the data resulting in a total study population of 1,000 patients. In a previous conducted pilot study by the UHNT (registered at ClinicalTrial.gov: NCT02146560), 300 patients undergoing major elective noncardiac surgery were included and disability was assessed by the WHODAS 2.0 after 6 months. The incidence of troponin elevation in this pilot was 14.1%. We do however expect an incidence of 11.0% as patients included in the pilot were mainly vascular patients, who are more

prone to have postoperative troponin elevations⁴. The mean WHODAS 2.0 in patients with an elevation in troponin was 29% compared to 15% in patients without troponin elevation. Based on these results, and using a level of significance of 0.05 and a power of 0.8 we expect 104 patients with troponin elevation. As the ratio between troponin elevation and no troponin elevation is $0.89/0.11 = 8$, we need to include 832 patients. We expect a dropout of 20% (based on the number of patients who did not fill out the WHODAS 2.0 after 6 months in the pilot study), leading to a final sample size of approximately 1,000 patients.

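### The hypothesis is about an independent association, but the only PMI versus no-PMI analysis of WHODAS 2.0 named in 7.2 is unadjusted, and the planned adjusted model is not designated as decisive

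*Combined protocol and SAP*

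**What the plan says.** The Introduction states the primary hypothesis: "any postoperative troponin elevation regardless of its association with MACE or noncardiac MAPE is independently associated with an increased risk of death and disability". The primary objective in section 2.1 uses the same qualifier for the subtypes: "To investigate and compare the independent prognostic effect of the different PMI phenotypes (myocardial infarction and NITE) and noncardiac MAPE on disability". Section 5.1.1 counts death as full disability (100%), so the WHODAS 2.0 score can carry both parts of the hypothesis.

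Section 7.2 opens with this comparison: "The primary outcome, postoperative WHODAS 2.0 after 6 months, will be compared among patients with and without PMI". The method is a t-test or a Mann-Whitney test, without covariates. The section then turns to biomarkers, taken before surgery, after surgery and as change, both as continuous values and split at thresholds: "Combination(s) of different biomarkers and the biomarker by itself in association with postoperative WHODAS 2.0 will be performed". The last sentence of the section brings in adjustment: "Multivariable linear regression analyses will be performed to adjust for potential confounders including age, gender, comorbidities (cardiovascular risk factors), preoperative WHODAS 2.0 score, RCRI". Its list of confounders closes with the surgical specialty. That sentence names no exposure.

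Section 4.4 takes its effect from the pilot study: "The mean WHODAS 2.0 in patients with an elevation in troponin was 29% compared to 15% in patients without troponin elevation". It uses significance level 0.05 and power 0.8, and mentions neither an SD nor any covariate. Section 7.1 applies 0.05 to every analysis and does not say which one decides the hypothesis.

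**The concern.** This is an observational cohort, so patients with PMI may differ from the others before surgery. The plan expects this. Section 4.4 notes that vascular patients have troponin elevation more often, and 7.2 lists preoperative WHODAS 2.0, RCRI and surgical specialty among the potential confounders.

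An unadjusted comparison of 6-month scores mixes any effect of PMI with the disability that patients brought to surgery. It cannot show independence. The adjusted analysis that could show it is planned, but the plan does not tie it to PMI yes/no or give it precedence. The two results answer different questions and may disagree, and the plan does not say in advance which one answers the hypothesis.

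**Working it through.** **Step 1. The passages side by side.**

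| Place | Exposure | Adjusted? | Said to decide the hypothesis? |
|---|---|---|---|
| Introduction, hypothesis | any troponin elevation | independent association required | – |
| 2.1 objective | MI, NITE, noncardiac MAPE | independent effect required | – |
| 4.4 sample size | troponin elevation yes/no | no, crude means | – |
| 7.2, first paragraph | PMI yes/no | no | not stated |
| 7.2, last paragraph | biomarkers, single and combined | yes | not stated |

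For disability-free survival, a secondary endpoint, 7.3 mentions the PMI phenotypes and a multivariable logistic model in one sentence. The primary endpoint has no equivalent.

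**Step 2. The plan's own figure.** For 104 patients with elevation against 832 without, 80% power and two-sided 0.05, the SD that fits a 14-point difference is

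SD = 14 / [(1.960 + 0.842) × √(1/104 + 1/832)] = 14 / (2.802 × 0.1040) ≈ 48.

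On a 0–100 scale with means 29 and 15, the SDs cannot exceed √(29×71) = 45.4 and √(15×85) = 35.7, or about 36.9 pooled. The figure of 104 therefore cannot be reproduced on this reading, and 4.4 supplies no usable SD. That is a separate matter, but it means the SD below has to be assumed.

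**Step 3. The crude test when PMI has no independent effect.** From the documents: 1,000 patients, 20% dropout and 11% PMI give 1,000 × 0.8 = 800 evaluable, of whom 800 × 0.11 = 88 have PMI and 712 do not. Assumed: SD 20 or 30, correlation ρ between preoperative and 6-month score of 0.5 to 0.7, and a preoperative gap of g points.

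- Spurious 6-month difference: b = ρ × g.
- Standard error: SE = SD × √(1/88 + 1/712) = SD × 0.1130, which is 2.26 at SD 20 and 3.39 at SD 30.
- Chance of p < 0.05: Φ(b/SE − 1.96) + Φ(−b/SE − 1.96).

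Example with g = 6, ρ = 0.5, SD 20: b = 3, b/SE = 1.33, chance 26%. With ρ = 0.7: b = 4.2, b/SE = 1.86, chance 46%.

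| Preoperative gap | SD 20, ρ 0.5–0.7 | SD 30, ρ 0.5–0.7 |
|---|---|---|
| 0 | 5% | 5% |
| 3 | 10–15% | 7–10% |
| 6 | 26–46% | 14–24% |
| 9 | 51–80% | 26–46% |

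A simulation of 4,000 studies per setting (SD 20 to 25, ρ 0.4 to 0.6) shows the same pattern. The crude test was significant in 11–27% of studies at a 5-point gap and in 29–74% at 10 points. The PMI coefficient adjusted for preoperative WHODAS 2.0 was significant in 4–6% throughout.

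**Step 4. Power of the adjusted coefficient.** Use SE = SD × √[(1 − R²y)/(1 − R²x)] × √(1/88 + 1/712). Here R²y is the share of outcome variance explained by the covariates (assumed 0.2 to 0.4) and R²x the share of PMI explained by them (assumed 0.1 to 0.3). With SD 20 to 30, power is at least 97% for an independent effect of 14 points, 49–97% for 7 points and 28–77% for 5 points.

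**The case against.** The strongest reply is that the adjusted analysis is already there. Section 7.2 plans a regression with preoperative WHODAS 2.0 and other confounders, and 7.3 refers back to those confounders as belonging to the primary analyses. One of the biomarkers is high-sensitive troponin. Taken alone and split at a threshold, it would come close to an adjusted test of any troponin elevation. A crude comparison followed by an adjusted model is also an ordinary sequence in a cohort study.

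Much of this stands. A reader might infer that the hypothesis is tested only crudely, or that a significant t-test will be taken as confirmation. The documents support neither reading: the regression is planned, and no passage says that the crude test decides. Section 4.4 does not name a test either; that it rests on a crude contrast follows from the two unadjusted means.

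What remains is the missing link. The Introduction defines PMI by troponin I above the 99th percentile. Section 5.3 measures high-sensitive troponin in addition to the routine troponin I, because it detects more infarctions. Dichotomised high-sensitive troponin is therefore not the same variable as PMI, and the reader has to guess which assay, threshold and time point would stand for it. Belonging to the primary analyses is also not the same as deciding the hypothesis.

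The percentages are open to fair criticism too. The baseline gap drives them and no figure in the documents supports any value of it. The adjusted 5% is partly built in, because preoperative WHODAS 2.0 is the only confounder simulated. Deaths scored as 100% are not modelled.

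**Conclusion.** The point holds as a gap in designation. The hypothesis and objective concern independence. The one named PMI versus no-PMI analysis of the primary outcome is unadjusted, and the sample size rests on a crude difference. The planned regression could answer the question, but it has no stated PMI term and no stated precedence.

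A significant crude result could therefore reflect baseline differences. Under the assumptions above, the chance of this with no independent effect runs from 7% (3-point gap, SD 30, ρ 0.5) to 80% (9-point gap, SD 20, ρ 0.7), and stays at 5% if there is no preoperative gap. These figures illustrate the mechanism and do not estimate what will happen in this cohort. It would go too far to conclude that the plan will declare the hypothesis confirmed on the crude test.

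**What to change.** In 7.2, state that:

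- the primary hypothesis is decided by the PMI (yes/no) coefficient with its 95% CI, at two-sided 0.05, from the already planned multivariable linear model for 6-month WHODAS 2.0, including preoperative WHODAS 2.0 and the listed confounders, with PMI as the Introduction defines it;
- for the primary objective, MI, NITE and noncardiac MAPE are entered as exposure terms in the same model family. Since PMI is either MI or NITE, these two terms replace the single PMI term in that second model;
- the t-test or Mann-Whitney comparison is descriptive.

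In 4.4, add that the stated power refers to the crude difference.

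The cost is wording in two sections. Section 5.1.3 already collects the covariates, and the model type is already planned. The real downside is that the adjusted effect will probably be smaller than 14 points. If it is near 5 to 7 points, power could fall well below 80% under the assumptions in Step 4, and the plan should say so openly.

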7.3 Secondary study parameter(s)

- Disability free survival will be described as percentages with their accompanying 95% confidence interval (CI) among patients with or without PMI. Different combinations of elevation in biomarkers will be tested. Comparison between different PMI phenotypes will be performed using chi-square test or Fisher's exact and multivariable logistic regression

analyses will be done to take several covariates into account, which are similar to confounders described for the primary analyses.

- Similar to disability free survival, MACE (including PMI and NITE), noncardiac MAPE and all-cause mortality will be presented as proportions with their accompanying 95% CI. Multivariable logistic regression analyses will be performed using MACE, noncardiac MAPE or all-cause mortality as outcomes, both in-hospital events and at 6 months (except for noncardiac MAPE as these will not be measured at 6 months). Different combinations of elevations in biomarkers (preoperative, postoperative and change between pre- and postoperative) will be tested against these outcomes to uncover correlations between particular combinations of elevated biomarkers to assess what disease entities are related to the outcome.
- A Kaplan-Meier method will be used to assess whether the cumulative incidence of 6-month mortality differs between patients with and without PMI. The probabilities of 6-month mortality between patients with and without elevation in (one or more) biomarker(s) will be compared using log-rank tests provided assumptions for this test are met. Cox-proportional hazard analyses will be performed to examine whether (one or a combination of several) biomarker(s) are associated with 6-month mortality adjusted for potential confounders.

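### The hypothesis is that troponin elevation matters regardless of MACE or noncardiac MAPE, but the with/without-PMI comparisons pool all PMI and no model in section 7 names an in-hospital event term

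*Combined protocol and SAP*

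**What the plan says.** - **Hypothesis (section 1):** "any postoperative troponin elevation regardless of its association with MACE or noncardiac MAPE is independently associated with an increased risk of death and disability".
- **Primary objective (section 2.1):** to "investigate and compare the independent prognostic effect of the different PMI phenotypes (myocardial infarction and NITE) and noncardiac MAPE on disability".
- **Test named for PMI on disability (section 7.2):** 6-month WHODAS 2.0 "will be compared among patients with and without PMI, using Student's t-test or a nonparametric Mann Whitney U test". The sample size in section 4.4 rests on the same pooled contrast (means of 29% and 15%).
- **Comparison named for PMI on mortality (section 7.3):** a Kaplan-Meier analysis of "whether the cumulative incidence of 6-month mortality differs between patients with and without PMI". The log-rank test in that paragraph is named for biomarker elevation.
- **Adjustment (section 7.2):** linear regression with "potential confounders including age, gender, comorbidities (cardiovascular risk factors), preoperative WHODAS 2.0 score, RCRI and surgical specialty". The logistic models in 7.3 use similar covariates.

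In sections 7.2 and 7.3 in-hospital MACE and noncardiac MAPE appear as outcomes, and MAPE is also listed among the PMI phenotypes. Neither is named as a covariate, an interaction term or a stratum, and no analysis is restricted to event-free patients.

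**The concern.** The hypothesis and the objective ask what troponin elevation adds apart from the events it accompanies. The with/without-PMI comparisons ask whether all PMI patients together differ from all others. On the protocol's own account these are different questions:

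- About one third of PMI is myocardial infarction (section 1), and non-fatal infarction is a MACE component (section 5.1.2).
- Section 1 also ties PMI to arrhythmia, pulmonary embolism, sepsis, respiratory failure and renal failure.
- Death counts as full disability on the WHODAS (section 5.1.1), so fatal events enter the primary outcome directly.

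The pooled groups could therefore differ even if isolated elevation carried no excess. At stake is whether the report may say that elevation is prognostic in its own right, or only that it travels with events that lead to disability.

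**Working it through.** **The plan's own figure.** Section 4.4 gives 0.89/0.11 = 8.09, taken as 8, and 104 × 8 = 832; 832 × 1.2 = 998, about 1,000. No SD is stated, so the 104 cannot be re-derived from the stated inputs. The argument does not depend on it.

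**Inputs from the documents.** 1,000 patients, 20% dropout and 11% PMI (section 4.4); one third of PMI is MI, and 19% of surgical patients have a MAPE (section 1).
- Analysed: 1,000 × 0.8 = 800.
- PMI: 0.11 × 800 = 88. No PMI: 712.

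**Assumed inputs (not in the documents).** Residual SD 25; 20%, 30% or 40% of NITE patients have an event; an event raises 6-month WHODAS by D = 10, 20 or 30 points; no effect of elevation itself.

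**Event shares.** In PMI, p1 = 1/3 + 2/3 × NITE share. In non-PMI, p0 = (0.19 − 0.11 × p1)/0.89.

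| NITE share | p1 | p0 | gap |
|---|---|---|---|
| 20% | 0.467 | 0.156 | 0.311 |
| 30% | 0.533 | 0.148 | 0.386 |
| 40% | 0.600 | 0.139 | 0.461 |

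**Pooled difference from events alone** = D × gap. **Power** ≈ Φ(difference/SE − 1.96), with SE = S × √(1/88 + 1/712) and S² = 25² + D² × the weighted mean of p(1 − p).

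Worked example, 30% share and D = 20: difference 20 × 0.386 = 7.7; S² = 625 + 400 × 0.14 = 681, so S = 26.1; SE = 26.1 × 0.113 = 2.95; power = Φ(2.62 − 1.96) = 74%.

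| D | Difference (points) | Pooled test significant |
|---|---|---|
| 10 | 3.1 to 4.6 | 19% to 37% |
| 20 | 6.2 to 9.2 | 56% to 88% |
| 30 | 9.3 to 13.8 | 85% to 99% |

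Weaker inputs shrink this. With event shares of one third and 19% and D = 10, the difference is 10 × 0.143 = 1.4 points. It is detected in only 7% to 10% of trials at SD 30 to 20 (104 vs 832 patients).

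**Conditioning on events.** In a simulation of 2,000 trials per setting (104 vs 832, SD 20 to 30, D = 20 or 30, no effect of elevation itself), the pooled t-test was significant in 17% to 99%. With an event term in the model, or in event-free patients only, the figure was 4% to 6%.

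**Precision of the isolated contrast.**
- Event-free PMI patients: 88 × (1 − p1) = 47, 41 or 35.
- Event-free non-PMI patients in the middle case: 712 × (1 − 0.148) = 607.
- 95% CI half-width: 1.96 × 25 × √(1/41 + 1/607) = 7.9 points, against 1.96 × 25 × √(1/88 + 1/712) = 5.5 for the pooled contrast.
- Utrecht alone (400 analysed, about 20.5 vs 303.5): 1.96 × 25 × √(1/20.5 + 1/303.5) = 11.2 points.

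**The case against.** **The hypothesis can be read another way.** Any elevation, regardless of what accompanies it, may mean that all elevations count. The pooled contrast then matches, and section 4.4 is built on it. This reading is fair, and it is why the pooled comparison should stay. It does not supply the independent effects of MI, NITE and noncardiac MAPE that section 2.1 asks for.

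**The detection rates are not false positives.** A reader might infer that the pooled test has an inflated type I error. It does not: in every setting above the pooled groups truly differ, so the rates are power for a real total association. Infarction is also itself a troponin elevation, and counting its harm under events builds in part of the result.

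**Events may follow from the injury.** Troponin is measured on days 1-3, while events accrue over the whole stay. An elevated value also triggers an ECG and an anesthesiologist consultation (section 5.3), and noncardiac MAPE includes unplanned ICU and medium care admission (section 5.1.2). Conditioning on events conditions on variables that may come after the exposure. This stands: the event-conditioned estimate is a direct association and cannot replace the total one.

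**The plan is not wholly pooled.** Disability free survival is compared by phenotype, biomarker combinations are modelled, and the confounder list is open-ended. A reader might infer that every adjusted model tests the pooled contrast; the documents do not support that. Yet none of these analyses is specified to condition on in-hospital events. Even with MI, NITE and noncardiac MAPE as separate terms, non-MI MACE would stay within the NITE effect.

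**Conclusion.** The point holds as a gap between the question and the specified analysis. Section 7 names no analysis that could show that elevation is associated with disability or death apart from MACE and noncardiac MAPE. The pooled comparison is valid as a total association and is not an error in itself.

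The structural point needs no assumed numbers. Its size does: about 3 to 14 points from events alone, detected in roughly 20% to 99% of trials, rests on an assumed SD, NITE event share and effect per event, and on a MAPE rate for surgical patients in general. Only the most extreme setting comes near the 14 points seen in the pilot (29% vs 15%). A reader might infer that events explain the pilot difference; nothing in the documents shows that.

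**What to change.** 1. **Section 7.2.** Keep the pooled PMI comparison and label it the total association. Add one covariate-adjusted model for 6-month WHODAS with separate terms for MI, NITE, non-MI MACE and noncardiac MAPE. MI needs its own term because every MI is both PMI and MACE.
2. **Definition.** State that MACE follows section 5.1.2. Section 7.3 describes MACE as including PMI and NITE, and under that wording the group with elevation but no MACE is empty.
3. **Key contrast.** Report, with a 95% CI, NITE without any in-hospital event versus neither PMI nor event. Base any regardless-of or independent conclusion on it. With main effects only, the NITE coefficient equals this contrast only if the NITE effect is the same with and without events; a NITE-by-event interaction or an event-free subset avoids that assumption.
4. **Section 7.3.** Do the same for 6-month mortality as far as the number of deaths allows.
5. **Interpretation.** State that events may lie on the pathway, so this contrast is a direct association.

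The cost is SAP wording and one extra model per outcome on data already collected. The real price is precision: about 35-47 isolated-elevation patients and about ±8 points at SD 25. The difference detectable with 80% power is about (1.96 + 0.84) × 25 × √(1/41 + 1/607) = 11 points. With Utrecht data alone the interval widens to about ±11. Section 4.4 was not sized for this contrast, and the SAP should say so.

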- b. Noncardiac MAPE including sepsis, renal failure, unexpected intensive care unit (ICU) admission and respiratory disorders.
- c. All-cause mortality

3. To examine whether (combinations of) perioperatively measured biomarkers are associated with 6-month MACE and all-cause mortality in patients undergoing elective noncardiac surgery.
4. To assess the added value of the perioperatively measured biomarkers on top of the currently used Revised Cardiac Risk Index (RCRI) to predict MACE after noncardiac surgery.

Study design

This prospective observational cohort study includes patients, aged 60 years and older, undergoing elective intermediate or high risk noncardiac surgery under spinal or general anesthesia with an expected postoperative hospital admittance of at least 24h. All patients are required to visit the preanesthesia outpatient clinic for preoperative consultation. In addition to care as usual, extra blood samples will be taken preoperatively and postoperatively up to three days after surgery to determine the following biomarkers: high sensitive troponin, brain natriuretic protein, C-reactive protein, creatinine and hemoglobin. At postoperative day 2, extra to routine care noninvasive imaging (i.e. electrocardiography and transthoracic echography) will be performed. Preoperatively measured biomarkers are considered baseline measurements. Biomarker values will be blinded from treating physicians in case this particular biomarker was not measured in routine care. In-hospital MAPE will be monitored including cardiac events, respiratory failure, pulmonary embolism, sepsis, renal failure and mortality. In addition, patients will be asked to fill out the WHODAS 2.0 questionnaire preoperatively and 6 months after their surgery to assess disability. Their general practitioners (GPs) will be approached to determine whether MACE and/or mortality have occurred during the 6 months follow up after surgery.

Study population

Patients aged >60 years undergoing elective intermediate (e.g. hip replacement) or high risk (e.g. liver resection) noncardiac surgery under general or spinal anesthesia with a postoperative hospital stay of at least 24 hours are eligible for participation in this study. We aim to include 500 patients in this study. Approximately 1,200 patients undergo elective major noncardiac surgery each year in the UMC Utrecht. Taking into account nonparticipation and potential lower inclusion rates at the

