- The added prognostic value of each of the biomarkers (or combinations of biomarkers) will be tested to predict MACE, both in-hospital and at 6-months. The biomarkers will be analyzed as continuous variables and using predefined clinical thresholds to define whether that particular biomarker is elevated. Multivariable logistic regression analyses will be performed using the predictors of the RCRI (i.e. high risk surgery, history of cerebrovascular disease, history of myocardial infarction, congestive heart failure, elevated creatinine and insulin dependent diabetes) as predictors together with the addition of elevation in biomarkers. Discrimination and calibration of the prediction models will be assessed using the c-statistic, Hosmer-Lemeshow test. The net reclassification index (NRI) and the Integrated Discrimination Index (IDI) will be calculated to quantify how well the updated RCRI reclassifies patients as compared to the traditional RCRI.

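### Models that use the pre-to-post biomarker change as an exposure should also include that marker's preoperative value, which sections 7.2 and 7.3 do not secure

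*Combined protocol and SAP*

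**What the plan says.** Section 7.2 relates biomarkers to the 6-month WHODAS 2.0 in three forms: "the preoperative, postoperative and the change (meaning difference between pre- and postoperative measurements) in biomarkers are of particular interest". Change is the plain difference between the two measurements. On scale, "The biomarkers will be analyzed both as continuous variables and using predefined clinical thresholds". The linear regressions are to "adjust for potential confounders including age, gender, comorbidities (cardiovascular risk factors), preoperative WHODAS 2.0 score, RCRI and surgical specialty". The baseline of the outcome is therefore in the list. The baseline of the exposure is not.

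Section 7.3 extends this:

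- Disability free survival is adjusted for covariates "which are similar to confounders described for the primary analyses".
- For MACE, noncardiac MAPE and mortality, "Different combinations of elevations in biomarkers (preoperative, postoperative and change between pre- and postoperative) will be tested against these outcomes".
- The Cox models ask whether biomarkers "are associated with 6-month mortality adjusted for potential confounders", without naming the confounders.

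The preoperative values will exist. The Summary states: "Preoperatively measured biomarkers are considered baseline measurements". Section 5.1.3 lists all five blood markers preoperatively, and section 5.3 describes a sample drawn just before induction. The only preoperative laboratory value that enters the adjustment indirectly is creatinine, as one dichotomous RCRI item ("congestive heart failure, elevated creatinine and insulin dependent diabetes").

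**The concern.** A difference is built from its own baseline, so the two are usually correlated. A regression on change alone therefore gives change part of the credit or blame that belongs to the preoperative level. Chronic elevation of troponin or BNP could plausibly be related to later disability in its own right.

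Section 7.3 wants these models to show which disease entities lie behind an outcome, and the objectives speak of independent prognostic effects. Both need a chronically raised level to be separated from a perioperative rise. A change coefficient fitted without baseline does not do that. Because its bias depends on variances and correlations not known in advance, a reader of the results could not correct for it.

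**Working it through.** The plan gives no figure to reproduce here. The check is algebra, followed by simulation under stated assumptions.

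**Inputs.** From the documents: the three exposure forms and the covariate list (7.2, 7.3), and n = 800, which is the combined 1,000 less 20% dropout (4.4). Assumed, because the documents are silent: k = SD(post)/SD(pre), rho = corr(pre, post), the effect sizes and the residual SD.

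**Algebra.** Let E[Y] = b0·pre + b1·post and D = post - pre. Then E[Y] = (b0 + b1)·pre + b1·D.

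- With pre in the model, the coefficient of D is b1. This is also the coefficient of post adjusted for pre, so those two models are equivalent.
- Without pre, the coefficient of D is b1 + (b0 + b1)·F, where F = Cov(pre, D)/Var(D) = (rho·k - 1)/(1 + k² - 2·rho·k).

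The bias vanishes if rho·k = 1 or b0 = -b1. With b0 + b1 positive, it is downward for rho·k < 1 and upward for rho·k > 1.

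**Only the preoperative level matters** (b0 = beta, b1 = 0). The correct change slope is 0, and the fitted one is F·beta:

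| k | rho | F |
|---|---|---|
| 1 | any below 1 | (rho - 1)/(2 - 2·rho) = -0.50 |
| 1.5 | 0.5 | -0.25/1.75 = -0.14 |
| 1.5 | 0.7 | 0.05/1.15 = +0.04 |
| 2 | 0.5 | 0/3 = 0 |
| 2 | 0.7 | 0.4/2.2 = +0.18 |
| 2 | 0.85 | 0.7/1.6 = +0.44 |

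**Both levels matter** (b0 = 2, b1 = 1, so the correct change slope is 1). At k = 1 the fitted slope is 1 + 3·(-0.5) = -0.5, a reversed sign. At k = 2 and rho = 0.7 it is 1 + 3·0.182 = 1.55. At equal SDs the general result is (b1 - b0)/2, so the sign of a positive b1 reverses only when b0 exceeds b1.

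**Can the named covariates stand in for baseline?** Simulation with n = 800, 2,000 replicates, b0 = 2, b1 = 1, rho = 0.7 and residual SD 6, adding an RCRI-like covariate correlated 0.3 with pre:

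| k | D alone | D + RCRI-like covariate | D + pre |
|---|---|---|---|
| 1 | -0.51 | -0.40 (negative in 90% of replicates) | 0.99 |
| 2 | 1.54 | 1.50 | 1.00 |

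**False positives.** Assume a pre-only effect of 5 points per SD and residual SD 20. At k = 1, change tested alone is significant at 0.05 in about 48%, 76% and 93% of studies for rho = 0.85, 0.7 and 0.5. At k = 1.5 and rho = 0.7 the rate is about 6%, and at k = 2 and rho = 0.5 it is 5%. At k = 2 and rho = 0.85 it is about 97%, with a positive slope. Adding pre returns the rate to about 5% throughout.

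**The case against.** The strongest reply is that the plan is silent here and has not decided against baseline adjustment. The covariate list is introduced as open, combinations of pre, post and change elevations are foreseen in 7.3, and the Cox confounders are unspecified. A reader might infer that the plan excludes the preoperative value, and the documents do not support that. What stands is narrower: nothing secures its inclusion, and an analyst following the named list would leave it out.

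A second reply is that RCRI, comorbidities and preoperative WHODAS 2.0 may carry part of the baseline effect. They may, but RCRI brings in only dichotomised creatinine and nothing for troponin, BNP, CRP or hemoglobin. In the simulation an RCRI-like covariate removed little of the bias.

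A third reply is that the effect may be small. That is correct for some values: where rho·k is near 1 there is almost none. A reader might infer from the equal-SD case that a rise will look protective in this study. The documents give no biomarker SDs or correlations, so neither that direction nor any false-positive rate is established.

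Finally, the exact collinearity of pre, post and change holds only for continuous terms. Dichotomised versions are not exactly collinear, so a blanket ban on using all three would go too far. The slope formula likewise does not carry over to thresholded change in logistic models, although the reason to hold the baseline constant does.

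**Conclusion.** The point holds for the association models in 7.2 and 7.3 that take biomarker change as an exposure. Run on the named covariates, a continuous change coefficient estimates b1 + (b0 + b1)(rho·k - 1)/(1 + k² - 2·rho·k) instead of b1. Over the assumed values above, a pre-only effect beta yields a spurious slope between -0.5 beta and +0.44 beta. The result rests on a linear model and on assumed k and rho, so the direction and size for this study are unknown.

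It does not reach the t-test or Mann-Whitney comparison of WHODAS 2.0 between patients with and without PMI, which is the contrast behind the sample size in 4.4. A reader who took the main comparison to be invalid would be going beyond the documents. This is a nearly free improvement to one group of models and does not undermine the study.

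**What to change.** Add to 7.2 and 7.3:

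- Any association model with a continuous change or postoperative blood biomarker as exposure also includes that marker's preoperative value, on a prespecified scale.
- Continuous pre, post and change are not entered in one model, because change = post - pre makes them exactly collinear.
- Where change is dichotomised, the preoperative value is likewise included.
- The Cox models for 6-month mortality follow the same rule.

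Log transformation of skewed markers is a reasonable option for the prespecified scale, but it is a separate choice and this repair does not need it.

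The cost is a few lines of text and one covariate per model, using the pre-induction sample already planned at Utrecht in 5.3. For Toronto, 4.4 states only that the eligibility criteria are the same, so confirm that an equivalent baseline sample is collected there before relying on the pooled cohort. Ideally the wording is settled before the batch assay results become available.
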